# 4.0 STUDY DESCRIPTION

# **4.1** STUDY OBJECTIVES

The primary objective of the study is to assess the effect of AXS-05 versus bupropion as measured by MADRS (Montgomery-Åsberg Depression Rating Scale).

The secondary objectives of the study include assessment of the effect of AXS-05 versus bupropion on:

- QIDS-SR-16 (Quick Inventory of Depressive Symptomatology-Self- Rated);
- CGI-I (Clinical Global Impressions–Improvement);
- CGI-S (Clinical Global Impressions-Severity);
- •
- C-SSRS (Columbia Suicide Severity Rating Scale); and
- Safety as assessed by AEs, vital signs, and laboratory assessments.

# **4.2** STUDY TREATMENTS

In this double blind study, subjects will be randomized, in a 1:1 ratio, to one of the following two treatment groups:

Treatment Group	Description
1. AXS-05	105 mg bupropion, 45 mg dextromethorphan tablet, oral
2. Bupropion	Bupropion SR 105 mg matching tablet, oral

# 4.3 STUDY DESIGN

This study is a randomized, double-blind, active-controlled, Phase 2 trial, consisting of a screening period of up to 4 weeks, and a 6-week treatment period.

#### **Screening Period**

Prior to randomization, all subjects will enter an up to four-week screening period (Screening) to determine eligibility. Eligible subjects must meet the Diagnostic and Statistical Manual of Mental Disorders, Fifth Edition (DSM-5) criteria for MDD without psychotic features, based on the Structured Clinical Interview for Diagnostic and Statistical Manual of Mental Disorders, Fifth Edition, Clinical Trials Version (SCID-5-CT), with a current major depressive episode of at least 4 weeks in duration. Eligible subjects must meet all other inclusion and no exclusion criteria.

#### **Treatment Period**

#### Randomization

Subjects who successfully complete Screening will be randomly assigned at the baseline visit (Baseline) to receive either AXS-05 or bupropion sustained release (SR) in a 1:1 ratio for 6 weeks. The randomization schedule will be computer-generated using a permuted block algorithm that will randomly allocate the study drug to randomization numbers.

The study will evaluate only subjects whose diagnosis of MDD with a current major depressive episode of moderate or greater severity is confirmed by an independent assessor based on clinical review . However, to maintain the blinding of the study

investigators, all subjects will be randomized to receive study medication and be included in the safety analysis.

#### Treatments

Doses will be titrated as follows:

- Days 1 3
  - AXS-05 group: 105 mg bupropion, 45 mg dextromethorphan QD
  - Bupropion group: 105 mg bupropion QD
- Days 4 42
  - AXS-05 group: 105 mg bupropion, 45 mg dextromethorphan BID
  - Bupropion group: 105 mg bupropion BID

All QD doses will be taken in the morning, orally on an empty stomach (at least 2 hours pre- or 2 hours post-prandial) with water. All BID doses will be taken at least 8 hours apart, orally on an empty stomach (at least 2 hours pre- or 2 hours post-prandial) with water. All study drug is of identical appearance and similar weight in order to maintain the integrity of the blind.

#### Assessments and Visits

Study visits will occur at Screening (Visit 1), Baseline (Day 0, Visit 2), and on Days 3, 7, 14, 21, 28, 42 and 49 (Visits 3 - 9). Study procedures and assessments will be performed during study visits as outlined in the Schedule of Assessments. Visit 3 (Day 3) will be conducted telephonically. Subjects will be reminded during Visit 3 to begin BID dosing on Day 4. All subjects completing 6 weeks of treatment or subjects prematurely discontinuing from the study will be required to complete a follow-up visit one week after the last dose of study drug, Visit 9, telephonically. Assessments will include safety parameters,

#### MADRS, QIDS-SR-16, CGI-S and CGI-I.

Study drug compliance will also be assessed at the 80% level by counting the number of tablets dispensed and returned. Noncompliant subjects are subject to early termination from the study.

Details of study design, including the schedule of all assessments, can be found in the protocol.

# 4.4 RANDOMIZATION AND BLINDING

In this parallel-group randomized study, subjects who meet study entry criteria will be randomly assigned in a 1:1 ratio to AXS-05 or to bupropion. The randomization schedule will be computer generated using a permuted block algorithm that will randomly allocate the study drug to randomization numbers.

No one involved in the study performance will have access to the randomization schedule before official unblinding of treatment assignment. No subject will be randomized into this study more than once.

Detailed blinding and unblinding procedures can be found in Section 8.7 of the protocol.

# 5.0 ANALYSIS POPULATIONS

## 5.1 RANDOMIZED POPULATION

The randomized population will consist of all subjects who complete the Screening Phase and are randomized to a treatment arm.

#### **5.2** SAFETY POPULATION

The safety population will include all subjects who have received study medication. Analyses based on this population will group subjects according to the treatment they actually received regardless of the treatment they were randomized to receive. All safety analyses will use the safety population.

#### 5.3 MODIFIED INTENT-TO-TREAT POPULATION

Based on the Modified Intent-to-Treat (mITT) population will consist of all subjects with a diagnosis of MDD and a current major depressive episode of moderate or greater severity, confirmed by an independent assessor, who are randomized, subsequently take at least 1 dose of the study drug, and have at least 1 post-Baseline assessment. The efficacy analysis will be based on this mITT population.

#### 5.4 PER PROTOCOL POPULATION

The Per Protocol population will include all subjects in the mITT population with no major protocol violations. Major protocol violation criteria will be established prior to the database lock. Protocol

AXSOME Therapeutics, Inc.	CONFIDENTIAL	Version 1.0—11 December 2018
AXS-05-MDD-201 SAP	Page 8 of 16	

deviations will be presented in the clinical study report. Efficacy analyses may also be performed based on the per protocol population.

## **6.1** DEFINITION OF BASELINE

Unless otherwise stated, the last observed measurement on the date of randomization will be considered the baseline measurement. If multiple observations are made during baseline, the baseline will be defined as average of the observations obtained during the baseline phase.

#### 6.2 SOFTWARE

Most analyses will be conducted using

#### **6.3** CHANGES TO PLANNED ANALYSES

Draft versions of the SAP will be numbered sequentially as Version 0.0i. The final approved version will be numbered as Version 1.00. Revisions after the "Final" version will be numbered as Version 1.0x. The Clinical Study Report will document any changes made after the final version approved before unblinding.

# 7.0 DESCRIPTION OF THE STUDY POPULATIONS

All tables, figures, and listings must include a population descriptor (e.g., mITT, safety or Per Protocol) in the title.

## 7.1 DISPOSITION

AXSOME Therapeutics, Inc. AXS-05-MDD-201 SAP Subject disposition summaries will be presented by treatment arm and will include the number of subjects randomized, the number and percentage of randomized subjects in the safety, mITT, and Per Protocol (if applicable) populations, as well as the number and percentage of subjects who complete the study. The summaries will also include the reasons for early discontinuation from the study.

Disposition summaries will be presented for safety, Intent-to-Treat, and Per Protocol populations (if applicable) separately.

# **7.2** DEMOGRAPHIC AND BASELINE CHARACTERISTICS

A summary of demographics and baseline characteristics will be presented by treatment arm and overall for the mITT and safety populations. The demographic characteristics will consist of age, sex, ethnicity, and race using descriptive statistics.

Demographic data including age, race, ethnicity, region, and gender, as well as baseline clinical characteristics will be summarized. Age will be calculated based on the following conditional algorithm:

- Has the patient had his/her birthday this year?
  - Yes, then AGE = (year of informed consent) (year of birth).
  - No, then AGE = (year of informed consent) (year of birth) 1.

# 7.3 MEDICAL HISTORY

A medical history listing will be presented.

# **8.0** PRIOR AND CONCOMITANT MEDICATIONS

All medications recorded on the CRFs will be coded using the WHO DRUG Dictionary Enhanced March 2014. Prior and concomitant medications will be summarized by treatment arm in the safety population by anatomical therapeutic chemical (ATC) Class Level 4 and WHO Drug base substance preferred name.

Prior medications are defined as medications with stop dates occurring before the date of first administration of any study treatment component. Concomitant medications are defined as medications with start dates occurring on or after the date of first administration of any study treatment component and no more than 30 days after the last administration of any study treatment component. Medications with start and stop dates that bracket the date of first administration of any study treatment component will be summarized as both prior and concomitant medications.

Medications that clearly stopped prior to date of first administration of any study treatment component will be included in the prior medications table, and medications that clearly started on or after date of first administration of any study treatment component will be included in the concomitant medications table. All other medications will be included in both the prior and concomitant medications tables.

Prior and Concomitant medications will be summarized for the safety population.

AXSOME Therapeutics, Inc. AXS-05-MDD-201 SAP

# 9.0 EFFICACY ANALYSES

#### 9.1 PRIMARY EFFICACY VARIABLE: CHANGE FROM BASELINE IN MADRS

#### 9.1.1 DERIVATION OF PRIMARY EFFICACY VARIABLE

The primary efficacy variable will be derived based on MADRS (Montgomery-Åsberg Depression Rating Scale). The changes from baseline will be calculated as baseline – post baseline, therefore, the positive changes are indicative of improvement. Missing values will be imputed via last observation carried forward (LOCF) method.

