#### 9.1.2 PRIMARY ANALYSIS

Changes from baseline in MADRS will be analyzed using a Mixed Model with Repeated Measures (MMRM). This analysis of covariance mixed-effect model for repeated measures will include treatment (two levels: 1 indicating active treatment and 2 indicating the control), week (5 levels: Weeks 1 through 4 and Week 6), and treatment-by-week interaction as factors, baseline value as a covariate, and subject as a random effect. SAS default covariance structure (variance components) will be assumed. The MMRM with maximum likelihood estimation will utilize the following pseudo- SAS code for analysis:

The primary hypothesis testing will be overall treatment effects. However, for completeness treatment difference at each post baseline week will also be presented. Overall treatment effects, treatment effects at individual post baseline week, and the differences between treatment effects will be estimated using the least-square mean estimates and will be reported together with the 2-sided 95% confidence interval of the treatment differences.

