#### 9.1.3 HANDLING OF MISSING VALUES

Unless otherwise stated, missing values will be imputed via the LOCF method.

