- 24. Time to clinical improvement based on the CGI-I (score of 3 [minimally improved] or less)
- 25. Treatment effects in patients with severe depression based on MADRS (defined as MADRS  $\geq$  30,  $\geq$  35); severe or very severe depression based on QIDS-SR-16 (defined as QIDS-SR-16  $\geq$  16)
- 26. Treatment effects based on MADRS in patients who had ≥1 prior antidepressant treatments during the current major depressive episode
- 27.

   28.

Efficacy variables related to change from baseline will be analyzed via the methods outlined in the analysis for the primary efficacy variable.

AXSOME Therapeutics, Inc. AXS-05-MDD-201 SAP **CONFIDENTIAL** Page 12 of 16 CGI-I (Clinical Global Impression Scale-Improvement) is a 7-point scale (1= Very Much Improved and 7= Very Much Worse), and will be analyzed using Cochran-Mantel-Haenszel test using score=ridit option. Frequency of the categories will also be presented.

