## **10.3** LABORATORY ASSESSMENTS

Chemistry and Hematology, Urinalysis and Coagulation Profile will be assessed at Screening and Week 6. Summary statistics for these parameters will be presented by visit for the actual value and change from baseline for each test in each laboratory category (Hematology, Chemistry, Urinalysis, and Coagulation Profile). Shift tables will be presented for shifts from baseline lab categories to end of study laboratory category. The three laboratory categories will be: L (below lower bound of normal range), N (within normal range), and H (above higher bound of normal range).

If a lab value is reported using a non-numeric qualifier (e.g., less than ( $\leq$ ) a certain value, or greater than (>) a certain value), the given numeric value will be used in the summary statistics, ignoring the non-numeric qualifier.

If a subject has repeated laboratory values for a given time point, the value from the first evaluation at that time point will be used for summarization purposes. For the purpose of determining baseline, the last nonmissing observation on or prior to randomization will be used. The Week 6 values will be the last post-baseline value on or prior to Week 6.

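### MADRS is filled in by LOCF before the primary MMRM, with no observed-data analysis and no week assignment for early-termination ratings

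*SAP*

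**What the plan says.** SAP 9.1.1 defines the primary variable as change from baseline in MADRS and closes its derivation with the rule "Missing values will be imputed via last observation carried forward (LOCF) method". SAP 9.1.3 makes the same method the default: "Unless otherwise stated, missing values will be imputed via the LOCF method". SAP 9.1.2 then fits a maximum-likelihood mixed model with treatment, week, their interaction, baseline and a random subject effect. Week has five levels (1, 2, 3, 4 and 6), and "SAS default covariance structure (variance components) will be assumed". On the contrast to be tested: "The primary hypothesis testing will be overall treatment effects". SAP 9.2 carries the approach to the other endpoints: "Efficacy variables related to change from baseline will be analyzed via the methods outlined in the analysis for the primary efficacy variable".

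The mITT population (SAP 5.3) takes subjects with an independently confirmed diagnosis "who are randomized, subsequently take at least 1 dose of the study drug, and have at least 1 post-Baseline assessment", so dropouts with one post-baseline assessment stay in.

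The protocol limits how much is missing. Section 7.3 encourages subjects who stop treatment to keep attending, and sections 8.11 and 9.1.5 give discontinued subjects a full Visit 8/ET assessment that includes MADRS. The schedule in 17.2 places ET in the Day 42 column. The SAP does not say which of the five weeks an ET MADRS belongs to. Its only readable rule for assigning a post-baseline value to a visit concerns laboratory data (SAP 10.3): "The Week 6 values will be the last post-baseline value on or prior to Week 6".

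The pseudo-code in 9.1.2 and secondary items 4, 27 and 28 are not shown in the public text, so any statement that something is absent is limited to what can be read.

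**The concern.** A likelihood-based repeated-measures model does not need complete data. Filling the gaps by LOCF first gives up that advantage and makes the model treat carried scores as measured ones. A subject lost after Week 1 supplies four carried values out of five to the primary contrast.

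The direction of the bias is conditional:
- If dropouts would have gone on improving, LOCF works against the arm with more or earlier dropout. It also shrinks a growing effect even when dropout is equal.
- If dropouts would have worsened, LOCF favours the arm with more dropout.
- With no effect, and dropout equal in rate, timing and relation to outcome, the bias is zero.

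Disposition tables by arm (Protocol 12.4.1.1, SAP 7.1) would reveal unequal dropout but not what it does to the estimate. The optional Per Protocol analysis (SAP 5.4) changes the population, not the missing-data method. Protocol 12 and SAP 3.0 both say the SAP will set out how missing data are handled, and on ET ratings it does not.

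**Working it through.** 1. **Inputs.** From the documents: five post-baseline visits, about 30 subjects per arm, two-sided 0.05. Protocol 12.2 and SAP 9.5 give no effect size, SD, power or dropout rate, so the plan has no figure to reproduce and every size below rests on assumptions. Assumed mean improvement at Weeks 1, 2, 3, 4, 6 is 5, 8, 10.5, 12, 14 (continuing) or 5, 7.5, 9, 9.5, 10 (plateau). Dropout is independent of outcome. The last scheduled visit is Week 1/2/3/4 in proportions 0.4/0.3/0.2/0.1 (early) or the reverse (late). The overall effect is the equal-weight mean of the five visit differences.

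2. **Loss per dropout under LOCF.** For a subject last seen at visit k, the loss is (1/5) × Σ over later visits j of (m_j − m_k). For the continuing trajectory:
   - Week 1: (3 + 5.5 + 7 + 9)/5 = 4.9
   - Week 2: (2.5 + 4 + 6)/5 = 2.5
   - Week 3: (1.5 + 3.5)/5 = 1.0
   - Week 4: 2/5 = 0.4
   - Early average: 0.4×4.9 + 0.3×2.5 + 0.2×1.0 + 0.1×0.4 = 2.95
   - Late average: 0.1×4.9 + 0.2×2.5 + 0.3×1.0 + 0.4×0.4 = 1.45

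3. **Bias at 30% v 10% dropout, no true effect.** Bias = (0.30 − 0.10) × loss, so 0.59 (early) or 0.29 (late). If an ET rating equals the next visit's mean, is placed there and is then carried, the losses become 2.5, 1.0, 0.4 and 0. The early average is 1.38 and the late average 0.57. With ET midway to the next visit the early average is 2.165.

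| Trajectory, timing | No ET | ET midway | ET at next visit |
|---|---|---|---|
| Continuing, early | 0.59 | 0.43 | 0.28 |
| Continuing, late | 0.29 | 0.20 | 0.11 |
| Plateau, early | 0.34 | – | 0.12 |
| Plateau, late | 0.14 | – | 0.04 |

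4. **Equal 20% dropout, early in one arm and late in the other.** 0.20 × (2.95 − 1.45) = 0.30. With ET at the next visit, 0.20 × (1.38 − 0.57) = 0.16.

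5. **True effect 1, 2, 3, 4, 5 (mean 3.0), equal 20% early dropout.** Losses of effect are 2.0, 1.2, 0.6, 0.2, averaging 1.30, so the expectation is 3.0 − 0.20×1.30 = 2.74. With ET at the next visit the average is 0.70 and the expectation 2.86.

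6. **Opposite case: dropouts lose 3 points, linearly, by Week 6.** LOCF overstates each dropout by 1.32, 1.05, 0.8 or 0.6, averaging 1.06 (early) or 0.82 (late). Times 0.20, this favours the arm with more dropout by 0.21 or 0.16. An observed-data model that projects the continuing trajectory errs the same way by more: 0.20 × (2.95 + 1.06) = 0.80 or 0.20 × (1.45 + 0.82) = 0.45.

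7. **Simulation.** 6,000 trials per scenario, 30 per arm, SDs 6, 7, 7.75, 8.25, 9, correlation 0.85 per week, baseline SD 4 with slope 0.3. The model SE is about 1.7, so 0.59 is about 0.35 SE and 0.28 about 0.16 SE.
   - Type I error, 30%/10% early, LOCF v observed: 6.7% v 6.6% (planned covariance) and 5.8% v 4.8% (unstructured) without ET; 5.9% v 6.0% and 4.9% v 4.8% with ET in its own window. Monte Carlo SE is about 0.3 points.
   - Power in the setting of step 5, unstructured, LOCF v observed: 33.0% v 39.3% without ET, 36.6% v 39.8% with ET. Monte Carlo SE is about 0.6 points.

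8. **Where the ET rating goes.** Take a subject with Week 1 improvement 3 and an ET improvement of 5 on Day 11. The five-visit mean is (3+3+3+3+5)/5 = 3.4 if ET counts as Week 6, (3+5+5+5+5)/5 = 4.6 if it counts as Week 2 and is carried, and 3.0 if it is unused. At trial level (30%/10% early, no effect), LOCF with ET labelled Week 6 gives an overall bias of 0.49, against 0.28 with ET in its own window; the Week 6 bias is 0.77 either way. With an observed-visits unstructured fit, labelling ET as Week 6 still leaves 0.28 overall and 0.77 at Week 6. Placing it in its own window leaves 0.00 and 0.02.

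9. **Separate check with other assumptions** (improvement 3, 6, 8, 10, 12; dropout uniform after Weeks 1–4; true effect 3.0; no ET). The expected LOCF estimate is 2.8 at 20%/20%, 2.26 with 30% dropout on AXS-05 and 10% on bupropion, and 3.34 with the reverse. Observed-data fits averaged 2.98, 3.01 and 3.00.

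**The case against.** The strongest reply is that the remedy swaps one untestable assumption for another. On these figures the largest LOCF bias is 0.59, while the observed-data model can be off by 0.80 if dropouts deteriorate. The documents give no dropout pattern to decide between the two. The comparison is also tilted: apart from the worsening case, dropout is assumed unrelated to outcome, a setting in which the observed-data model is unbiased by construction. Dropout for adverse events or lack of effect was not simulated. This stands, and it is the reason to keep a labelled sensitivity analysis rather than rely on the observed-data fit alone.

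Other points that stand in part:
- The protocol asks for ET ratings, so the with-ET figures are the more realistic ones: at most 0.43, about a quarter of an SE.
- Type I error is not an argument against the plan.
- Under the planned LOCF, the ET mapping moves the overall bias by only 0.21 (0.49 v 0.28). The larger contrast appears once the model is fitted to observed visits.
- The simulations lose dropouts from 30 per arm, whereas Protocol 12.2 plans 30 compliant completers per arm. With 43 and 33 randomised the SE is about 1.5, which makes 0.59 slightly larger in SE units (0.39).
- The covariance structure is a separable choice; removing LOCF does not by itself require an unstructured matrix.
- The protocol's stated objective is safety, and this is a small Phase 2 trial, which limits the severity.

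None of this supplies an observed-data analysis or an ET rule.

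**Conclusion.** The concern holds. On the readable text, LOCF enters the primary MADRS variable before the MMRM and extends to the other change-from-baseline endpoints. No analysis shows the result without it, and ET ratings have no assigned week. That LOCF precedes the model is inferred from the order of 9.1.1 and 9.1.2, since the pseudo-code is not shown.

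Confidence is high on the text and on the conditional direction. The size is uncertain because dropout, trajectories and SDs are all assumed, and unequal dropout is a scenario rather than a prediction. In the scenarios examined, the systematic error is a fraction of an SE, and the power loss with equal 20% early dropout is roughly 3 to 6 percentage points. Because the defect sits in the primary analysis and costs little to repair, it should be fixed before database lock.

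**What to change.** - Delete the LOCF sentence from SAP 9.1.1, and exempt the change-from-baseline MMRMs in 9.2 from 9.1.3.
- Fit those models to observed visits without imputation. An unstructured within-subject covariance is preferable, with a named fallback if it does not converge.
- Assign each ET MADRS to the analysis window containing its actual study day, not automatically to Week 6. The protocol's ±2-day visit windows leave Days 1–4, 10–11, 17–18, 24–25 and 31–39 uncovered, so contiguous windows are needed. One option by nearest scheduled day is Days 1–10, 11–17, 18–24, 25–35, and 36 onward. State which rating counts when a window holds two.
- Keep LOCF, or a delta-adjusted analysis, as a labelled sensitivity analysis.
- Whether ratings after treatment discontinuation are used, and the missing-data rule for responder and remission endpoints, remain the sponsor's choice but should be written down.

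The cost is SAP wording, with no change to data collection. At 30%/10% dropout under an unstructured covariance and without ET, the model SE moves from 1.73 to 1.75 overall and from 2.33 to 2.52 at Week 6. With ET in its window it stays at 1.72 overall and moves from 2.30 to 2.48 at Week 6. The price in assumptions is reliance on missing at random.
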